Inclusion Criteria

Potential subjects must meet ALL of the following criteria:

- 1. Signed Informed Consent Form
- Male and female subjects aged 18-70 years, inclusive; 2.
- Good general health and good oral health based on the opinion of the study 3. investigator;
- All maxillary natural anterior teeth (teeth #6 through #11) must be present; 4.
- 5. Availability for the duration of the study;
- Minimum average Vita Extended Bleachedguide 3D-Master 6. shade score of 17 ≥ or darker.

Exclusion Criteria

Potential subjects must **NOT HAVE ANY** of the following conditions:

- Presence of orthodontic appliances and/or any anterior tooth with a prosthetic 1. crown, veneer, or deemed non-vital:
- Obvious signs of periodontal disease, rampant caries, or any condition that the dental examiner considers exclusionary from the study.
- Five or more carious lesions requiring immediate care. 3.
- Concurrent participation in another oral clinical study. 4.
- Self-reported pregnant and/or lactating women.
- History of allergies or sensitivity to tooth whitening products, hydrogen peroxide, personal 6. care consumer products, or their ingredients;
 - Restorations on the teeth to be scored which may interfere with scoring procedures.
- Have used professional whitening products within one (1) year and/or had dental 8. prophylaxis (professional dental cleaning) within thirty (30) days prior to the start of the study.

III. STUDY DESIGN

1. Configuration

This randomized, examiner-blind, single-center clinical study features a three-cell, parallel-group design to explore the use of a new in-office whitening technology compared to two existing technologies. Patients will be randomized to one of three study groups, and will undergo in-office whitening treatments according to their assigned group.

2. Duration

Subjects' participation in the study will consist of two (2) visits to the clinical research site during approximately 7 days duration of the study: Screening/Baseline, Day 7.

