^{*}At each visit, on-site brushing will occur before all clinical shade examinations

IV. STUDY PRODUCTS / TREATMENTS

Study subjects will be randomly assigned to one of the three (3) following products for professional in-office application:

- Beaming White 25%HP Gel (test)
- Philips Zoom Chairside Light-Activated Whitening System 25% HP Gel (control)
- Opalescence Boost PF 40%HP Gel (control)

For daily oral hygiene through the duration of the study all study participants will be provided with:

- Colgate Cavity Protection Toothpaste
- Colgate adult soft-bristled toothbrush

V. PROCEDURES

Visit 1a (Screening/Baseline):

1.Initial Screening and Selection of Subjects

Prospective candidates will report to the clinical facility where they will sign an Informed Consent Form (Appendix II), Privacy Notice (Appendix III), Photo Release (Appendix IV), and complete a Medical History/Oral Health Questionnaire (Appendix V). They will be screened by the study examiner to identify those subjects who meet the inclusion/exclusion criteria. The findings of this initial screening procedure will be recorded on the Initial Screening Form (Appendix VI).

The first 180 subjects who meet the inclusion/exclusion criteria, sign an Informed Consent Form/Privacy Notice and photo release, and complete a health questionnaire will be entered into the study.

2.Oral Soft and Hard Tissue Assessment

All subjects will receive a visual evaluation of their oral soft and hard tissues. This examination will be performed by a study dentist and will include an evaluation of the lips, soft and hard palate, gingival mucosa, buccal mucosa, mucogingival fold areas, tongue, sublingual and submandibular areas, salivary glands, the tonsilar and pharyngeal areas, and teeth. The results of this evaluation will be recorded on the Oral Soft and Hard Tissue Assessment Form (Appendix VII).

3. On-site brushing

Subjects will be asked to perform a supervised on-site brushing with water at each visit immediately prior to having the shade of their teeth graded.

4. Tooth Shade Assessment

[figure not shown]
Candidates will be screened by the study examiner to evaluate the tooth shade (color) of the maxillary right central incisor, lateral incisor, and canine, as well as for the maxillary left incisors and canine (teeth numbers 6, 7, 8, 9, 10, and 11). Tooth shade will be assessed by the principal investigator, using the Vita Extended Bleachedguide 3D-Master Shade Guide.

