The Vita Extended Bleachedguide 3D-Master includes 29 tabs arranged and numbered by the manufacturer from 1 to 29 (lightest to darkest). Both sets of tabs will be used to assign a shade score to each maxillary anterior tooth. All maxillary anterior teeth must each have a minimum score of a 17 according to the Vita Extended Bleachedguide 3D-Master. Individual tooth shade scores will be recorded on the Tooth Color Examination Form (Appendix VIII).

The methods employed for tooth shade assessments are outlined in Appendix I (Tooth Shade Assessment Guidelines).

5. Extraoral Photos

In a subset of subjects (approximately 5/cell), extraoral photos will be taken using a handheld SmileLite MDP2 system with an attached smartphone. The patient's position will be kept as consistent as possible. Photos will be taken prior to product application, with the retractor in place and no gingival barrier, and will be repeated once more after all sessions are completed and the gingival barrier is removed (again with the retractor in place).

6. Randomization and In-office Whitening

Study subjects will be randomly assigned to one of the three (3) study groups. In-office whitening will then be performed according to the product instructions. This procedure will vary depending on which group the subject is assigned to. An overview of application guidelines for each product is included in Appendix XII.

7. Questionnaire

Subject and provider will complete the relevant portions of a short questionnaire.

Visit 1b: Immediately post-whitening:

1. Oral Soft and Hard Tissue Assessment

All subjects will receive a visual evaluation of their oral soft and hard tissues. This examination will be performed by a study dentist and will include an evaluation of the lips, soft and hard palate, gingival mucosa, buccal mucosa, mucogingival fold areas, tongue, sublingual and submandibular areas, salivary glands, the tonsilar and pharyngeal areas, and teeth. The results of this evaluation will be recorded on the Oral Soft and Hard Tissue Assessment Form (Appendix VII).

U.S.IRB

OCT - 7 2025

On-site brushing

Subjects will again be asked to perform a supervised on-site brushing with water for 2 minutes. Afterwards, they will be instructed to rinse with water thoroughly. Shade examination should be done approximately 5 minutes after rinsing, to allow for re-hydration of the tooth surface.

3. Tooth Shade Assessment

The methods employed for tooth shade assessments will be repeated.

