4. Extraoral Photos

For the same subset of subjects, a final photo will be taken after whitening is completed, using the same techniques as before (with retractor in place, and no gingival barrier).

5. Questionnaire

Subject and provider will complete the relevant portions of a short questionnaire.

6. Study Product Distribution:

All subjects enrolled in the study will be provided with a soft-bristled adult toothbrush and toothpaste for home use. Subjects will be instructed to brush their teeth twice daily (morning and evening) for two (2) minutes each time with the toothpaste and toothbrush provided. All subjects will be instructed to repeat the same procedure twice daily for the duration of this study.

7. Instruction to Subjects

Subjects will be instructed to use only the products (toothpaste and toothbrush) provided during the study period, and to refrain from using any other oral hygiene products and from routine dental treatment (except emergency) during the course of the study. Subjects who receive dental treatment and/or use medication must report this to the study investigators. The use of tooth whitening products is prohibited. There will be no restrictions regarding diet during the course of the study. Subjects will be asked to return to the clinical facility 1 week post-treatment for subsequent clinical examinations.

Example of Label Instruction for both test and control groups (Appendix XI):

CRO-2025-09-WHT-MS

Product (Letter Code)

Brush your teeth twice daily (morning and evening) for two (2) minutes each time. Cover the entire length of the bristled head with toothpaste. Do not swallow. For investigational use only by the study participant. Not for Retail Sale. For Adult Use Only. Keep out of reach of children under 6 years.

In case of emergency or for further information telephone:

[name] at [contact]

Visits 2: (7 days +/- 3 days after Baseline):

1. Visit Form

After 7 days of study product use at home, all subjects will report back to the clinical site for their follow-up appointment. The study examiner will complete a Study Visit Form (Appendix IX) to account for health updates and/or adverse reactions.

2. Subsequent Oral Soft and Hard Tissue Assessment

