All subjects will return to the dental clinic, and receive an evaluation of their oral soft and hard tissues. The same examination and recording procedure employed at the previous visit will be repeated. The results of this evaluation will be recorded on the Oral Soft and Hard Tissue Assessment Form (Appendix VII). Any abnormal findings noted after the initial screening visit will be recorded as adverse events following the adverse event procedures listed below.

3. On-site brushing

Subjects will be asked to perform a supervised on-site brushing immediately prior to having the shade of their teeth graded.

4. Tooth Shade Assessment

The methods employed for tooth shade assessments will be repeated from the baseline appointment.

5. Extraoral Photos

In the subset of subjects, the methods employed for extraoral photos will be repeated from the baseline appointment.

6. Questionnaire

Subject and provider will complete the relevant portions of a short questionnaire.

Upon completion of the 7-day (final) visit, all subjects will discontinue product use and will return to their normal oral hygiene routine. An End of Study Visit Form (Appendix IX) will be completed for all subjects entered into the study even if they do not complete the entire 7-days duration of the study. Subjects will be interviewed with respect to adverse events and concomitant medications during the course of the study. All used and unused products should be returned to the clinical facility.

VI. DENTAL TREATMENT DURING THE STUDY

Subjects will be instructed to refrain from routine dental treatment (except emergency) during the course of the study. Subjects who receive dental treatment or use medication must report this to the study investigators.

Subjects will be interviewed with respect to adverse events and concomitant medications. Visit/End of Study Form (Appendix IX) will be completed for all subjects entered into the study even if they do not complete the entire duration of the study.

VII. STATISTICAL METHODS AND DATA ASSESSMENT

Safety Analysis

Safety endpoints will include adverse events and oral examinations. Subjects who discontinue the study due to adverse events will be presented in a subject listing, as well as in a summary table. Adverse events for which a causal relationship to study medication could not be ruled out, will also be reviewed and discussed in a narrative format.

Data Analysis

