APPENDIX XI LABEL INSTRUCTIONS

U.S. IRB LABEL INSTRUCTIONS FOR TOOTHBRUSH AND TOOTHPASTE

Toothbrush and Toothpaste will be placed in a ziploc bag with a label applied to the outside of the bag

CRO-2025-09-WHT-MS

Product (Letter Code)

Brush your teeth twice daily (morning and evening) for two (2) minutes each time. Cover the entire length of the bristled head with toothpaste. Do not swallow. For investigational use only by the study participant. Not for Retail Sale. For Adult Use Only. Keep out of reach of children under 6 years. In case of emergency or for further information telephone: [name] at [contact]

LABEL INSTRUCTIONS FOR IN-OFFICE PROFESSIONAL WHITENING

CRO-2025-09-WHT-MS

Product (Letter Code)

Follow manufacturer's instructions, detailed in appendix XII.

For investigational use only by a dental professional. Not for Retail Sale. For Adult Use Only. Keep out of reach of children under 6 years. In case of emergency or for further information telephone: [name] at [contact]

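### The Visit 2 order and an undefined letter code on identical home kits leave an avoidable risk of unmasking the shade grader

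*Combined protocol and SAP*

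**What the plan says.** Section III.1 sets the level of masking: "This randomized, examiner-blind, single-center clinical study features a three-cell, parallel-group design". Of the whitening step, Section V (Visit 1a, item 6) says: "This procedure will vary depending on which group the subject is assigned to". Appendix XII describes an LED mouth tray for the test system, a lamp aligned to the retractor for Zoom, and a red gel with no light step for Opalescence Boost. The primary outcome (Section VII) is tooth shade read by eye against the Vita guide.

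Section V lists Visit 2 in this order:
- Item 1, Visit Form: "The study examiner will complete a Study Visit Form (Appendix IX) to account for health updates and/or adverse reactions".
- Item 2, soft and hard tissue examination.
- Item 3, brushing: "Subjects will be asked to perform a supervised on-site brushing immediately prior to having the shade of their teeth graded".
- Item 4, shade assessment.
- Items 5 and 6, photos and questionnaire.

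On who grades, Section V (Visit 1a, item 4) first gives the shade evaluation to the study examiner and then states: "Tooth shade will be assessed by the principal investigator, using the Vita Extended Bleachedguide 3D-Master Shade Guide". The Synopsis lists the principal investigator and the examiner as separate entries. Appendix I requires one examiner for all assessments.

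For the home kits, Appendix XI states: "Toothbrush and Toothpaste will be placed in a ziploc bag with a label applied to the outside of the bag". That label has a product letter-code field. At the end of Visit 2: "All used and unused products should be returned to the clinical facility".

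The only safeguard is in Section XIII, where investigators undertake in general terms to try to stay blinded to the regimen.

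**The concern.** A visual shade match is a judgement, and the examiner blind is its main protection. Subjects know whether they had a tray, a lamp or no light. If the grader asks a subject about reactions and then grades, a passing remark can identify or narrow the arm before the primary reading is made.

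The label is a second possible route. A letter serves no evident purpose on a toothbrush and toothpaste that are the same for everyone. If there is one letter per whitening arm, anyone who sees the bags could group subjects by arm.

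What is at stake is bias in the between-group shade comparison. Neither the ANCOVA nor a larger sample would remove it.

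**Working it through.** The plan gives no figure on this point to reproduce. The check is mainly a comparison of passages.

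**1. Can the grader be the person who completes the form?** Yes, on one reading. Section V gives the Visit Form to the study examiner and also names the study examiner as evaluating shade. The next sentence names the principal investigator as grader. If these are two people and the investigator grades, the form is not completed by the grader. The documents leave this open.

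**2. Does the form come before grading?** Section V and Section III.2 differ.

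| Source | Order at one week |
|---|---|
| Section V, Visit 2 | Visit Form, tissues, brushing, shade, photos, questionnaire |
| Section III.2 | Shade, tissues, adverse reactions, then images and questionnaire |

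No sentence makes either list binding, but Section V is the only step-by-step instruction the site has.

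**3. What does the form ask?** Appendix IX covers current medication, unexpected or serious reactions and treatment prescribed for them, dental treatment, newly prescribed medication, and pregnancy or breast-feeding. No readable item asks which whitening system was used. The answers come largely from the subject, so completing the form implies some conversation.

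**4. What is the letter?** The product table gives the code for the toothpaste and toothbrush as not applicable and marks the three whitening systems as blinded product. The home-kit label nevertheless has the same letter field as the in-office label (Appendix XI). Section III.3 says that the randomization list contains random product codes. No passage defines the letter, says that there is one per arm, or says that the grader sees the bag.

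**5. How many readings could be affected?** 180 × (1 − 0.10) = 162 at Day 7, or 60 × 0.90 = 54 per arm. (Section II prints about eighteen completers, which does not agree with 180 less 10%.)

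**6. What would a bias do?** This is an illustration on assumed inputs only; the plan gives neither a standard deviation nor a bias size. Take one pairwise comparison, no true difference, two-sided α = 0.05 (Section VII), and a differential grading bias of b standard deviations:

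se = √(2/54) = 0.192; rejection probability = Φ(b/se − 1.96) + Φ(−b/se − 1.96)

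| Assumed b (SD) | False-positive rate |
|---|---|
| 0 | 5.0% |
| 0.1 | 8.2% |
| 0.2 | 18.0% |
| 0.3 | 34.4% |
| 0.5 | 73.8% |

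If a 0.5 SD bias affects only part of one arm, b is the share times 0.5. A 10% share (b = 0.05) gives 5.8%, a 25% share (b = 0.125) gives 10.0%, and a 50% share (b = 0.25) gives 25.5%. These figures show why masking matters. They are no evidence that unmasking occurs.

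**The case against.** The case against is substantial, and much of it stands.

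- **The order is not binding.** Section III.2 puts shade first. Lists elsewhere are plainly not chronological: Table I places randomization below whitening, and the Visit 1a questionnaire is listed after whitening although its baseline item is for before treatment. This stands, so it cannot be said that every Day 7 reading follows the form.
- **A reader might infer that the examiner must interview each subject about the treatment received.** The documents do not support that. The text says only that the examiner completes a form. The separate sentence on interviewing subjects about adverse events names no role and comes after the numbered steps.
- **A remark need not reveal the arm.** Mention of a light would not separate the test system from Zoom, since both use one. It would rule out Opalescence Boost.
- **A reader might infer that the label exposes the arm, and that one disclosure would identify everyone else given that letter.** That would need one letter per arm, a grader who sees the bags and remembers the link, and other subjects still ungraded. None of this is stated. In the listed order, kits are handed out after grading at Visit 1b, and their return is mentioned after the Visit 2 steps.
- **A bias must differ between arms to matter.** This is correct. A uniform shift across three active arms would cancel in the comparison.
- **The questionnaires also carry a product code (Appendix XIII).** This is true, but at Visits 1b and 2 they are already listed after shade grading.

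These points limit the claim without removing it. Two sections disagree on the order, the grader is not settled, the letter has no stated purpose, and no procedure separates the form, the kit or the subject's conversation from the grading.

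**Conclusion.** The point holds as an avoidable risk of unmasking. It is not a demonstrated leak. The documents support three statements: Section V lists the form before the primary reading and gives it to a role that it also names as grader; Section III lists the reverse order; and identical home kits carry an undefined product letter.

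The size cannot be derived from the documents. The risk from the form applies to at most about 162 Day 7 readings, and only if the study examiner is the grader and the Section V order is followed. The risk from the label further requires that the letter stand for the whitening arm and that the grader see it. The change is worth making because it is nearly free and protects the primary endpoint, not because bias has been shown.

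**What to change.** - In Section V, Visit 2, put on-site brushing and shade grading before the Visit Form, adverse-event interview, questionnaire and kit return. This agrees with Section III.2.
- Instruct subjects not to discuss their treatment with the grader until grading is finished.
- On the toothbrush and toothpaste label (Section V, Visit 1b, item 7, and Appendix XI), replace the product letter code with the subject number.
- Reconcile the Synopsis, Section V (Visit 1a, item 4) and Appendix I on who the single shade grader is.

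The cost is a small change in visit flow and a new label, with no added visits, staff or measurements. One side effect needs care: Appendix IX also asks whether the answers justify excluding the subject's data from the analysis. Once the form follows grading, that item should be answered without regard to the shade scores.

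No change is needed at Visit 1b, where the questionnaire already follows grading. Nor need the adverse-event interview move to the treating staff, since that would have safety data collected by people who know the arm.

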The study will be monitored by members of the Oral Care Clinical Research Department of Colgate-Palmolive at periodic intervals during the course of the study to ensure that the study is being conducted according to Good Clinical Practice Guidelines.

General Procedures

The sponsor's study monitor will review the progress of the study as frequently as is necessary to ensure adequate and accurate data collection. Monitoring activities may include:

- Periodic on-site visits
- Telephone communications with the site
- Ongoing review of case report forms, clinical records, and administrative documents

All records pertaining to the study will be made available to the study monitor during each site visit. Routine monitoring visits will be planned and confirmed in advance, as much as possible, to allow adequate time to assemble these records. Unplanned visits may occur as dictated by study necessities.

Important agreements and discussions between the sponsor and investigator should be documented for the study file. Examples include: eligibility criteria exceptions, agreements to deviate from protocol-defined procedures, notifications of subject withdrawal, etc.

Reports

The final report for the sponsor will summarize the method, statistical analyses, data and conclusion relative to the test product, the subject completing the study, and summarize any adverse events and deviations. Source data will be retained by the study site. Copies of the transcribed data will be incorporated in the final report as data tables.

Record Retention and Access to Source Data/Documents

Source documents must be kept for at least five (5) years after terminating the study. The Investigator will maintain all study documentation for all subjects entered into the study in a secure area ensuring the confidentiality of the information collected. Securing records includes placing written forms in locked file cabinets and/or sealed and labeled storage boxes in a locked room. Access will be denied to all persons with the exception of the Principal Investigator and his/her designees. In the event that clinical records cannot be securely kept by the clinical site for the agreed to time, the study sponsor will be notified before the destruction of any study records occurs. The study sponsor maintains the right to keep the clinical records for the agreed time limit.

XIII. STUDY PRODUCT MANAGEMENT

Study Products

Study products will be supplied by the sponsor for this study. The study investigator will verify that the quantity of supplies, protocol number, and identification numbers match the information on the shipping invoice, and will store and account for the study supplies as described below.

Study Products Storage, Handling, and Accountability

The study products must be stored in a secure area with limited access, at room temperature. The investigator is directly responsible for the accountability of all used and unused study products. The investigator and all sub-investigators will make every effort to remain blinded as to the subject regimen. Records must be maintained to document the receipt and disposition of all study drug supplies provided to the investigator by the sponsor. The study monitor will review these records periodically during the course of the study. At the end of the study, or as directed by the monitor, the investigator must return all unused study products to the sponsor.

XIV. CONCOMITANT THERAPY

If a subject takes concomitant medications as a matter of necessity for the treatment of a medical condition, then such medication may be permitted for the duration of the study at the discretion of the investigator. However, it is the responsibility of the investigator to disqualify from entering the study any subject who, upon screening, is using medication or consumer products that might obscure the interpretation of study results. All medications currently used by the subject at enrollment, or any time through the end of the study, will be recorded on medical history and visit form. Subjects may receive medication to treat adverse events as deemed necessary by the investigator or the subject's physician.

XV. ADVERSE EVENTS

A. DEFINITIONS:

Adverse Events (AEs) and Serious Adverse Events (SAEs) are defined by the ICH Guideline for Good Clinical Practice (ICH GCP) as follows:

U.S. 1R8

Adverse Event: Any untoward medical occurrence in a patient or clinical investigations subject administered a pharmaceutical product and which does not necessarily have to have a causal relationship with this treatment. An adverse event (AE) can therefore be any unfavorable and unintended sign (including abnormal laboratory finding), symptom, or disease temporally associated with the use of a medicinal product, whether or not considered related to the medicinal product.

AEs include any clinically significant deterioration of a subject's medical status, after being enrolled in the study and signing an Informed Consent form. The AE may involve any organs or systems and can be represented by the new onset or the deterioration of a disease, a syndrome, a symptom, a physical sign, as well as by findings and results of instrumental examinations and laboratory tests. Any medically relevant and untoward change from baseline, including frequency or pattern changes for a fluctuating condition (e.g., migraine), occurring after the first administration of study medication is an adverse event. All such occurrences must be recorded and reported accordingly, whether they appear causally related to the study medication, or not.

Serious Adverse Event: Any adverse event occurring at any dose that results in any of the following outcomes:

- Death
- Life threatening adverse event
- Inpatient hospitalization, or prolongation of existing hospitalization
- Persistent or significant disability/incapacity
- Congenital anomaly/birth defect

Important medical events that may not result in death, be life-threatening, or require hospitalization may be considered a serious adverse experience when, based upon appropriate medical judgment, they may jeopardize the patient or subject and may require medical or surgical intervention to prevent one of the outcomes listed in this definition.

Examples of such important medical events include allergic bronchospasm requiring intensive treatment in an emergency room or at home, blood dyscrasias or convulsions that do not result in inpatient hospitalization, or the development of drug dependency or drug abuse.

B. IMPORTANT NOTES:

The concepts of Adverse Event / Experience (AE) and Serious Adverse Event / Experience (SAE) represent **regulatory** instruments used to evaluate and monitor the safety of clinical trial subjects. Therefore, these terms only apply in light of their regulatory definition. The term "serious", in a regulatory sense, does not necessarily mean "severe". All adverse events (serious and non-serious) reported during a study will be taken into account when analyzing the study data and establishing the safety profile of the investigational drug, and will be included in the final study report. The SAE concept is primarily used to identify, during the conduct of the trial, those adverse events that may require an expedited reporting procedure to regulatory authorities.

Death: The outcome of death requires that the AE that resulted in death be reported as an SAE. Death, in and of itself, is not an AE; it is only an outcome. The cause of death is the AE; therefore,

U.S. 1R8

the investigator should make every effort to obtain and document the cause of death for all subjects who die during the study. If, despite all efforts, the cause of death remains unknown, the AE should be documented as "unspecified fatal event".

Life-threatening Adverse Event: Any adverse event that places the patient or subject, in the view of the investigator, at immediate risk of death from the reaction as it occurred (*i.e.*, it does not include a reaction that had it occurred in a more severe form, might have caused death).

Hospitalization: It should be noted that hospitalization, in and of itself, does not represent an SAE. It is the adverse event leading to the subject's hospitalization that becomes "serious" when it requires inpatient care. Consequently, SAE should not be reported in case of pre-planned hospitalizations for pre-existing conditions that did not worsen during the study.

Disability: A substantial disruption of a person's ability to conduct normal life functions.

C. REPORT AND DOCUMENTATION OF ADVERSE EVENTS:

All adverse events forms are provided in Appendix X (Forms 105361 and 105362).

General Procedures for All Adverse Events

All clinical complaints, symptoms, or signs that meet the adverse event definition will be recorded on the Non Serious Adverse Events case report form (CRF) using a recognized medical term or diagnosis that accurately reflects the event. Source documentation should be maintained that allows for clear identification of each adverse event and the following parameters required for the CRF:

- AE description
- Date of onset
- Date of resolution
- Outcome
- Severity
- Seriousness
- Relationship to study drug (causality)
- Actions taken

Adverse events will be assessed by the investigator or designee for severity, relationship to the study product, possible etiologies, and whether the event meets the criteria as a serious adverse event and therefore requires immediate notification of the sponsor.

For CRF data collection purposes, the outcome of all adverse events recorded on the Adverse Event form should be reported within two (2) weeks of the study completion. The investigator will include this information in the Site Report providing a line listing using the Periodic/End of Study Report Form and attaching the individual adverse event form for each case reported. However, the investigator is responsible for following all adverse events until resolution or until no longer of clinical concern, and providing these data to the sponsor.

When protocol duration is six (6) months or longer, a Periodic/End of Study Report Form must be completed and included as part of your Site Report every six (6) months for the duration of the protocol.

OCT - 7 2025

Reporting Procedures for Serious Adverse Events

Any adverse event that is serious or potentially serious requires additional detailed reports and follow-up. A serious adverse event must be reported to the sponsor's representative immediately (within 24 hours). A Serious Adverse Event Report Forms must be completed so as to facilitate discussion and implementation of necessary follow-up measures, and to enable the sponsor to submit necessary reports to regulatory authorities and other investigators. Once the sponsor reviews the Serious Adverse Event Report Form, additional information may be requested from the investigator to allow appropriate medical evaluation and determine the regulatory reporting requirements.

The investigator is responsible for following all adverse events, especially those deemed "serious", until resolution or until the event is no longer of clinical concern, and for providing all data to the sponsor in an agreed-upon format. The investigator is also responsible for reporting all serious adverse events to the Institutional Review Board (IRB) overseeing the conduct of the study at the respective study center, according to the rules and procedures established by this committee.

SAE/SAR Reporting

Study Originator (SO) receives Form 105361 Adverse Event/Reaction Reporting Form for Non-interventional Studies from the investigator and forwards to [contact] and [contact] within one (1) calendar day (no later than 1 business day) of receipt.

Non-Serious AER Reporting

Study Originator (SO) receives the Form 105361 Adverse Event/Reaction Reporting Form for Non-Interventional Studies from the investigator for non-serious AER within one (1) calendar day (no later than 1 business day) of investigator awareness and forwards to [contact] and [contact] within one (1) calendar day (no later than 1 business day) upon receipt from investigator.

End of Study Reporting

Within 2 weeks of study completion the SO must complete Form 105362 Periodic/End of Study Report Form for Non-Interventional Studies on Humans documenting adverse event/reaction information reported during conduct of the study and submits it to [contact] and [contact].

XVI. PREGNANCY

No self-reported pregnant women will be enrolled in this study. In the event a woman enrolled in this clinical research study becomes pregnant during the course of the study, participation in this study will be terminated upon the clinical staff's notification of the event. The subject's medical records used in this study will be updated to reflect the pregnancy and there will be follow-up contact until the end of the pregnancy to record the outcome in the clinical file.

XVII. SUBJECT TERMINATION/WITHDRAWAL PROCEDURES

A genuine effort will be made to determine the reason(s) why a subject fails to return for the necessary visit(s) or is dropped from the study. Subjects could be dropped from the study if any of the following occur:

- 1. Subject fails to substantially comply with the protocol requirements.
- 2. Subject fails to report for a scheduled examination.
 - 3. Subject is treated with medication(s) during the course of the study, which may interfere with the parameters under study.
- 4. Subject receives emergency dental or medical treatment, which may interfere with the parameters under study.
- 5. Subject develops a serious adverse reaction. The Study Investigator will immediately notify the study monitor and information will be recorded on an Adverse Reaction Form (Appendix X).
- 6. Sponsor elects to terminate the study.
- 7. Subject elects to terminate participation in the study.

A study Visit Form (Appendix IX) indicating end of study participation must be completed for all subjects entered into the study even if they do not complete the study.

XVIII. NEW FINDINGS

Subjects will be informed of any significant new findings related to study products or procedures when they become known during the course of this clinical research study. Such information may affect the subject's decision to continue participation in the study.

U.S.IRB

U.S. 128 0C7 - 7 2025 400VED"

